
 To evaluate the efficacy of cobimetinib plus atezolizumab compared with pembrolizumab, as measured by OS and 2-year landmark OS To evaluate the efficacy of cobimetinib plus atezolizumab compared with pembrolizumab, as measured by ORR To evaluate the efficacy of cobimetinib plus atezolizumab compared with pembrolizumab, as measured by investigator-assessed PFS To evaluate the efficacy of cobimetinib plus atezolizumab compared with pembrolizumab, as measured by DCR To evaluate the efficacy of cobimetinib plus atezolizumab compared with pembrolizumab, as measured by DOR To evaluate the efficacy of cobimetinib plus atezolizumab compared with pembrolizumab, as measured by the change from baseline in HRQoL 	
 OS, defined as the time from randomization to death from any cause Two-year landmark survival, defined as survival at 2 years Objective response, defined as a complete response or partial response on two consecutive occasions ≥ 4 weeks apart, as determined by an IRC according to RECIST v1.1 Objective response, defined as a complete response or a partial response on two consecutive occasions ≥ 4 weeks apart, as determined by the investigator through use of RECIST v1.1 PFS, defined as the time from randomization to the first occurrence of disease progression, as determined by the investigator through use of RECIST v1.1, or death from any cause, whichever occurs first DCR, defined as the proportion of patients with a complete response, a partial response, or stable disease at 16 weeks, as determined by the IRC through use of RECIST v1.1 DCR, defined as the proportion of patients with a complete response, a partial response, or stable disease at 16 weeks, as determined by the investigator through use of RECIST v1.1 Duration of objective response, defined as the time from the first occurrence of a documented objective response to disease progression, as determined by an IRC according to RECIST v1.1, or death from any cause Duration of objective response, defined as the time from the first occurrence of a documented objective response to disease progression, as determined by the investigator through use of RECIST v1.1, or death from any cause, whichever occurs first The change from baseline in HRQoL scores, as assessed through use of the two-item GHS/QoL subscale of the EORTC QLQ-C30, at specified timepoints while receiving treatment

Table 1 Objectives and Corresponding Endpoints (cont.)

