3. STUDY DESIGN

3.1 DESCRIPTION OF THE STUDY

3.1.1 Overview of Study Design

Study CO39722 is a Phase III, multicenter, open-label, randomized study designed to evaluate the efficacy, safety, and pharmacokinetics of cobimetinib plus atezolizumab compared with pembrolizumab in treatment-naïve patients with advanced *BRAF*^{V600} wild-type melanoma. The patient population includes patients with locally advanced and unresectable or metastatic melanoma. *BRAF*^{V600} wild-type status will be determined using local testing, and enrollment based on local testing will be subsequently confirmed with central testing after enrollment. Patients who are enrolled based on *BRAF*^{V600} wild-type status by local testing may continue in the study even in cases when central testing gives a different result. If local test results are not available for enrollment, *BRAF*^{V600} wild-type status will be determined by central testing. PD-L1 status will be determined using central testing, with <1% immune cells ([IC] 0 vs. IC1, 2, 3) defined as being PD-L1 negative for PD-L1 status.

[figure not shown]
The primary objective of the study is to evaluate the efficacy of cobimetinib plus atezolizumab compared with pembrolizumab in treatment-naïve patients with advanced *BRAF*^{V600} wild-type melanoma, as measured by primary endpoint of PFS assessed by independent review.

This study will be conducted globally and approximately 450 patients will be randomized in a 1:1 ratio to one of two treatment arms:

- Arm A: Patients will receive 60 mg of cobimetinib by mouth (PO) on a 21 days on, 7 days off (21/7) schedule (dosing on Days 1–21, followed by no dosing on Days 22–28) plus 840 mg of atezolizumab by intravenous (IV) infusion on Days 1 and 15 of each 28-day cycle (n=225).
- Arm B: Patients will receive 200 mg of pembrolizumab administered by IV infusion every 3 weeks (Q3W) (n=225).

The study schema is presented in [Figure 3](#).

Figure 3 Study Schema

PD=progressive disease; PD-L1=programmed death–ligand 1; Q3W=every 3 weeks; Q2W=every 2 weeks, R=randomization; RECIST v1.1=Response Evaluation Criteria in Solid Tumors, Version 1.1; 21/7=21 days on/7 days off (schedule).

Stratification factors are PD-L1 status (IC0 vs. IC1, 2, 3), baseline serum LDH level (less than or equal to the upper limit of normal [ULN] vs. greater than the ULN), and geographic region (North America vs. Europe vs. Australia, New Zealand, and others).

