4.5.11 Patient-Reported Outcomes

To more fully characterize disease burden and clinical benefit of atezolizumab and cobimetinib in patients with advanced melanoma, patient-reported outcome (PRO) data will be obtained through use of the following instruments: EORTC QLQ-C30 and the EQ-5D-5L. The questionnaires will be translated as appropriate into the local language. Reminders will be provided in order to maximize compliance. It is critical to rigorously collect the PRO data as they support the secondary and exploratory efficacy endpoints.

The EORTC QLQ-C30 and EQ-5D-5L will be completed on Day 1 of Cycle 1 and every 4 weeks thereafter, including prior to tumor assessments visits every 8 weeks. In addition, the questionnaires will be completed at the site for the treatment discontinuation visit and at unscheduled visits. All PRO questionnaires must be completed prior to any study assessment(s) that could bias a patient's responses.

Also, the PROs will be collected every 4 weeks for 6 months after the treatment discontinuation visit. PRO data collected post-study treatment will be used as a unique opportunity to quantify patients' post-treatment experience in terms of humanistic outcomes.

Patients will use an electronic device to capture all PRO data. Instructions to use the device and to complete the PRO questionnaires will be provided by site staff once the patient is randomized and before initiation of study treatment. The data will be transmitted to a centralized database maintained by the vendor and will be made available for access by appropriate study personnel at the site. In the event that the device or the Web-based system is not readily available, paper questionnaires formatted for use as backup data collection forms should be used to minimize missing data. Compliance with data collection will be documented throughout the study.

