4.5.11.1 EORTC QLQ-C30

The EORTC QLQ-C30 is a validated, reliable self-reported measure (Aaronson et al. 1993; Fitzsimmons et al. 1999) that is commonly used in clinical trials involving patients with metastatic melanoma (Revicki et al. 2012; Schadendorf et al. 2015). It consists of 30 questions that assess five aspects of patient functioning (physical, emotional, role, cognitive, and social), three symptom scales (fatigue, nausea and vomiting, pain), GHS/QoL, and six single items (dyspnea, insomnia, appetite loss, constipation, diarrhea, and financial difficulties) with a recall period of the previous week. Scale scores can be obtained for the multi-item scales. The EORTC QLQ-C30 module takes approximately 10 minutes to complete. A 10-point change is defined as a clinically meaningful difference for the EORTC QLQ-C30 (Osoba et al. 1998) and has been used in other melanoma studies (Long et al. 2016; Shadendorf et al. 2015).

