- ^u After informed consent has been obtained but prior to initiation of study drug, only serious adverse events caused by a protocol-mandated intervention should be reported. After initiation of study drug, all adverse events will be reported until 135 days after the last dose of study drug or initiation of new anti-cancer therapy, whichever occurs first. After this period, all deaths, regardless of cause, should be reported (per Section 5.3.5.8). After this period, the Sponsor should be notified if the investigator becomes aware of any serious adverse event that is believed to be related to prior study drug treatment (see Section 5.6). The investigator should follow each adverse event until the event has resolved to baseline grade or better, the event is assessed as stable by the investigator, the patient is lost to follow-up, or the patient withdraws consent. Every effort should be made to follow all serious adverse events or adverse events of special interest considered to be related to study drug or trial-related procedures until a final outcome can be reported.
- ^v Archival tumor tissue with sample collection date < 5 years or fresh baseline tumor tissue will be collected during screening. An optional on-treatment biopsy will be obtained at Cycle 1, Day 15 (± 5 days), and a mandatory biopsy will be obtained at progression if clinically feasible.
- ^w PRO instruments, the EORTC QLQ-C30 and EQ-5D-5L, will be completed in this order using an electronic device on Day 1 of Cycle 1 and every 4 weeks (± 3 days) thereafter, prior to tumor assessments visits every 8 weeks, at the treatment discontinuation visit, and at unscheduled visits, as clinically indicated. Patients will also complete the questionnaires every 4 weeks for 6 months after treatment discontinuation. All PRO questionnaires are required to be completed prior to the administration of study treatment and/or prior to any other study assessment(s) that could bias a patient's responses.
- ^x The initial dose will be delivered over 60 (± 15) minutes. If the first infusion is well tolerated all subsequent infusions will be delivered over 30 (± 10) minutes until loss of clinical benefit. Study drug administration may be ± 3 days after the first cycle.
- ^y Medication diaries should be collected and reviewed and unused medications should be collected for assessment of compliance.

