Appendix 1 Schedule of Activities (cont.)

Table 1 Arm A: Cobimetinib Plus Atezolizumab Schedule of Assessments (28-Day Cycles)

^z Cobimetinib 60 mg/day PO will be given on a 21 days on/7 days off dosing schedule. Study drug administration may be ± 3 days after the first cycle, commensurate with atezolizumab administration.

^{aa} After treatment discontinuation, information on survival follow-up and new anti-cancer therapy (including targeted therapy and immunotherapy) will be collected via telephone calls, patient medical records, and/or clinic visits approximately every 3 months (unless the patient withdraws consent or the Sponsor terminates the study). If a patient requests to be withdrawn from follow-up, this request must be documented in the source documents and signed by the investigator. If the patient withdraws from study, the study staff may use a public information source (e.g., county records) to obtain information about survival status only.

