16. Have you been constipated?	1	2	3	4
17. Have you had diarrhea?	1	2	3	4
18. Were you tired?	1	2	3	4
19. Did pain interfere with your daily activities?	1	2	3	4
20. Have you had difficulty in concentrating on things, like reading a newspaper or watching television?	1	2	3	4
21. Did you feel tense?	1	2	3	4
22. Did you worry?	1	2	3	4
23. Did you feel irritable?	1	2	3	4
24. Did you feel depressed?	1	2	3	4
25. Have you had difficulty remembering things?	1	2	3	4
26. Has your physical condition or medical treatment interfered with your family life?	1	2	3	4
27. Has your physical condition or medical treatment interfered with your social activities?	1	2	3	4
28. Has your physical condition or medical treatment caused you financial difficulties?	1	2	3	4

For the following questions please circle the number between 1 and 7 that best applies to you

29. How would you rate your overall health during the past week?

1 2 3 4 5 6 7

Very poor Excellent

30. How would you rate your overall quality of life during the past week?

1 2 3 4 5 6 7

Very poor Excellent

Appendix 9

EuroQol 5-Dimension, 5-Level Questionnaire

Under each heading, please tick the ONE box that best describes your health TODAY

MOBILITY

- I have no problems in walking about
- I have slight problems in walking about
- I have moderate problems in walking about
- I have severe problems in walking about
- I am unable to walk about

SELF-CARE

- I have no problems washing or dressing myself
- I have slight problems washing or dressing myself
- I have moderate problems washing or dressing myself
- I have severe problems washing or dressing myself
- I am unable to wash or dress myself

USUAL ACTIVITIES (e.g. work, study, housework, family or leisure activities)

- I have no problems doing my usual activities
- I have slight problems doing my usual activities
- I have moderate problems doing my usual activities
- I have severe problems doing my usual activities
- I am unable to do my usual activities

PAIN / DISCOMFORT

- I have no pain or discomfort
- I have slight pain or discomfort
- I have moderate pain or discomfort
- I have severe pain or discomfort
- I have extreme pain or discomfort

ANXIETY / DEPRESSION

[figure not shown]
- I am not anxious or depressed
- I am slightly anxious or depressed
- I am moderately anxious or depressed
- I am severely anxious or depressed
- I am extremely anxious or depressed

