Appendix 10 Management of Cobimetinib plus Atezolizumab-Associated Adverse Events (Arm A)

Note: For information regarding management of atezolizumab-associated adverse events, please refer to [Appendix 11](#).

Guidelines for Management of Cobimetinib plus Atezolizumab Adverse Events

Event	Action to Be Taken
General guidance for dose modifications and treatment delays and discontinuation	
 • There will be no dose modifications for atezolizumab. • If atezolizumab is withheld and corticosteroids are initiated for an atezolizumab-related toxicity, corticosteroids must be tapered over ≥ 1 month to ≤ 10 mg/day oral prednisone or equivalent before atezolizumab can be resumed.^{a, b, c} 
The dose of cobimetinib can be reduced by 20 mg (one dose level) up to two times (i.e., from 60 mg to 40 mg and then from 40 mg to 20 mg). If further dose reduction is indicated after two dose reductions, the patient must discontinue cobimetinib but may continue treatment with atezolizumab at the investigator's discretion.
 
 • If cobimetinib is withheld for > 28 days because of toxicity, the patient should be discontinued from cobimetinib, unless resumption of treatment is approved by the Medical Monitor after discussion with the investigator. • After dose reduction, consideration may be given to allow for dose escalation of cobimetinib by a maximum of one dose level following resolution of the adverse event that resulted in dose modification, provided there are no safety concerns. • If atezolizumab is withheld for > 12 weeks because of toxicity, the patient should be discontinued from atezolizumab, unless resumption of treatment is approved by the Medical Monitor after discussion with the investigator.
IRRs, CRS, anaphylaxis, and hypersensitivity reaction	
 • Guidelines for management of IRRs and CRS are provided in the Atezolizumab Investigator's Brochure and Appendix 11 • For anaphylaxis precautions, see Appendix 7. • For severe hypersensitivity reactions, permanently discontinue all study treatment.

CRS = *cytokine-release syndrome*; IRR = infusion-related reaction.

^a If corticosteroids have been initiated, they must be tapered over ≥ 1 month to ≤ 10 mg/day oral prednisone or equivalent before atezolizumab can be resumed.

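### On the nominal calendar every scheduled on-treatment Arm A QLQ-C30 looks back on the week without cobimetinib, which limits how the secondary HRQoL comparison can be read; the SAP model behind that comparison also needs reconciling with the protocol

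*Protocol*

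**What the plan says.** **Timing.**
- Protocol 3.1.1 gives cobimetinib on Days 1–21 of each 28-day cycle, "followed by no dosing on Days 22–28".
- Protocol 4.5.11 sets the questionnaires: "The EORTC QLQ-C30 and EQ-5D-5L will be completed on Day 1 of Cycle 1 and every 4 weeks thereafter". Appendix 1, Table 1, footnote w allows ±3 days. It asks for completion before dosing and/or before other assessments that could bias the answers.
- Protocol 4.5.11.1 describes the QLQ-C30 as an instrument "with a recall period of the previous week". Item 30, one of the two global health items that form the endpoint, asks (Appendix 8): "How would you rate your overall quality of life during the past week".
- Table 1 of the protocol defines the secondary endpoint as change from baseline in the two-item global score "at specified timepoints while receiving treatment".
- Dosing can move. Footnote z says: "Study drug administration may be ± 3 days after the first cycle, commensurate with atezolizumab administration". Appendix 10 says: "If cobimetinib is withheld for > 28 days because of toxicity, the patient should be discontinued from cobimetinib", subject to Medical Monitor approval to resume.
- Arm B has 21-day cycles (protocol 4.3.2.3).

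**Model.** SAP 4.4.2.6 plans visit summaries and change from baseline, and sends the between-arm comparison to SAP 4.4.3.2.4. The permissive list of terms there is intercept, linear time, treatment and treatment-by-time. It lists no baseline score and names no covariance structure. Protocol 6.4.3 commits to mixed models with the baseline domain score among the covariates, and to LS means with between-arm differences and confidence intervals. SAP Sections 1 and 4 let the SAP override the protocol only for registration or filing.

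**The concern.** The questionnaire interval equals the Arm A cycle length, so each form meets the cobimetinib cycle at the same point, and that point is the end of the off week. In Arm B the 28-day interval and the 21-day cycle are out of step, so recall samples the whole cycle. The alignment affects one arm only, and neither document discusses it.

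Protocol 3.3.11 asks whether HRQoL holds up on the combination until progression, relative to pembrolizumab. If HRQoL falls on dosing days and partly recovers in the off week, the scheduled forms would show less loss in Arm A than patients experience over the cycle. If it does not recover, nothing is lost.

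The model text is a separate weakness. A straight line can misfit any curved course after baseline, a baseline covariate usually buys precision, and an unnamed covariance leaves a choice to be made after the data are seen. The SAP also speaks of score changes in 4.4.2.6 and of scores in 4.4.3.2.4, so the response variable is not settled.

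**Working it through.** The plan states no sample size, power or effect for HRQoL, so there is no figure of its own to reproduce.

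**1. Nominal calendar, Arm A.** Form k falls on study day 1 + 28k and recalls days 28k − 6 to 28k, which are cycle Days 22–28. Over 26 post-baseline forms, 0 of 26 × 7 = 182 recall days are dosing days. Dosing days are 21/28 = 75% of the cycle.

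**2. Visit window.** A form shifted by s days recalls cycle days 22 + s to 28 + s. Dosing days for s = −3 to +3:
- next cycle waits for the form: 3, 2, 1, 0, 0, 0, 0, total 6 of 49 = 12.2%;
- next cycle starts on Day 29 regardless: 3, 2, 1, 0, 1, 2, 3, total 12 of 49 = 24.5%.

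Both percentages assume visits spread evenly over the window. Appendix 2 carries a general ±7-day note. If it applied, a form 7 days early would recall Days 15–21, all dosing days. Footnote w is specific to the questionnaires and says ±3.

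**3. Dosing slip.** If dosing runs L days late against a fixed questionnaire calendar, recall covers cycle days 22 − L to 28 − L. Dosing days are L of 7 for L up to 7, and 7 of 7 for L = 7 to 21. The pattern then reverses.

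**4. Arm B.** Recall covers days 0–6, 7–13 and 14–20 after the last infusion at weeks 4, 8 and 12, and repeats at weeks 16, 20 and 24.

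**5. Possible size (illustration only).** Let d be the loss on dosing days and r the fraction recovered in the off week. Both are assumed; neither is in the documents.
- Cycle-average loss = 0.75d + 0.25d(1 − r).
- Measured loss with k dosing days in recall = d(1 − r) + (k/7)rd.
- Gap = (0.75 − k/7)rd.

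With d = 10 (the meaningful change in protocol 4.5.11.1) and r from 0 to 1:

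| Situation | k | Gap (points) |
|---|---|---|
| On schedule | 0 | 0 to 7.5 |
| Window average, dosing waits | 6/7 | 0 to 6.3 |
| Window average, dosing on Day 29 | 12/7 | 0 to 5.1 |
| 3 days early | 3 | 0 to 3.2 |
| Dosing 7–21 days late | 7 | 0 to −2.5 |

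For d = 5, halve these.

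**6. Baseline covariate (conditional).** These figures apply only if the SAP model turned out to be an unadjusted change-score model, which no section specifies. At one visit the variance is 2σ²(1 − ρ) unadjusted and σ²(1 − ρ²) adjusted, a reduction of (1 − ρ)/2: 35%, 25% and 15% at assumed ρ of 0.3, 0.5 and 0.7. For the mean of six visits, with equal correlations and complete data (both assumed), the reduction is (1 − ρ)² / [(1 + 5ρ)/6 + 1 − 2ρ]: 0.49/0.817 = 60%, 0.25/0.583 = 43% and 0.09/0.350 = 26%. There is little or no gain if baseline already enters as a time-zero response with a common mean.

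**The case against.** **On timing.** The endpoint is defined at specified timepoints, not as a cycle average, so the yardstick in step 5 is the reviewer's. A form on a common 4-week grid, normally before dosing, is a reasonable convention. Days 22–28 are not free of treatment: atezolizumab is infused on Day 15, so that week is 7–13 days after an infusion. No half-life or recovery course is given. Early visits, dose holds, delays and questionnaires at unscheduled visits all break the alignment, and adverse events are collected on Day 15 of each Arm A cycle.

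All of this stands as a limit on the size of the point. It does not remove the one-sided alignment, and adverse event records do not measure HRQoL.

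**On the model.** The SAP list is permissive, so silence on baseline is under-specification and not a decision to leave it out. Protocol 6.4.3 already commits to most of what is wanted. The SAP overrides it only for filing, SAP Section 1 ties filing to positive results, and SAP 2.5 records that the primary endpoint was missed. Both model descriptions sit under exploratory endpoints, so neither outranks the other on that ground. This also stands, and it is why the request is to reconcile the two texts.

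**On consequence.** HRQoL is outside the testing hierarchy in SAP 2.3 (OS, IRC-assessed ORR, landmark OS), and the trial is being terminated early. No decision rule changes.

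**Conclusion.** The calendar point is exact on the nominal schedule: 0 of 7 recall days are dosing days, and 12–24% under an even ±3-day spread, against 75% of the cycle. HRQoL while cobimetinib is being taken is hardly sampled in Arm A, and a statement that HRQoL was maintained must be read with that in mind.

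A reader might infer that the Arm A result is biased upward, by as much as 7.5 points. The documents do not support that. The figure needs full recovery in the off week and strict adherence to the calendar; the gap is zero without recovery and changes sign under a long dosing slip. This is an interpretive limit of unknown size.

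A reader might also infer that the SAP has dropped baseline adjustment at a cost of 26–60% in variance. That is not supported either: it presumes an unadjusted change-score model, assumed correlations and complete data. Whether the linear trend misfits depends on a post-baseline course that nobody has described. What holds is that the SAP model is loose, differs from protocol 6.4.3, and should be reconciled with it.

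The point is modest. It concerns interpretation and precision, not type I error.

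**What to change.** **(a) Model, SAP 4.4.3.2.4.** Model change from baseline with baseline score, categorical visit, treatment and treatment-by-visit. Name the covariance: unstructured, with a stated fallback such as compound symmetry if it does not converge. Report LS-mean differences by visit. Adding the final stratification factors is optional. State how this relates to protocol 6.4.3. Label the change post hoc, because SAP Version 3 already records the primary result. Cost: no new data or patients, only the post hoc label.

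**(b) Data already collected.** Summarise the day of each Arm A questionnaire relative to the last cobimetinib dose. Run a descriptive sensitivity analysis by dosing versus non-dosing recall days, noting that off-schedule patients may differ because of toxicity. State the limitation beside the HRQoL result. Cost: programming only, provided the diary dose dates (protocol 4.3.3) were entered in the database.

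**(c) Design point, too late for this trial.** Add a QLQ-C30 at Arm A Day 15, without replacing the existing forms, and at the same calendar weeks in Arm B. Recall there is Days 8–14, and Days 5–11 to 11–17 over ±3 days, so all 7 days are dosing days. Cost: about 10 minutes per patient per 4 weeks, the completion time in protocol 4.5.11.1. Arm A Day 15 is already a visit. Some matching Arm B weeks are not, so off-site completion would be needed (assuming the device allows it).
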